11.2 Clinical Laboratory Variables

Descriptive statistics for clinical laboratory values (in SI units) and changes from Baseline to Visit 16/ET as well as shift tables from Baseline to Visit 16/ET for quantitative variables will be presented by treatment group of the antecedent studies, current treatment (SHP465) for each enrollment type, and overall for the following clinical laboratory variables:

Biochemistry and Endocrinology

Total cholesterol	Calcium
Aspartate aminotransferase	Urate
Phosphorus	Blood urea nitrogen
Alanine aminotransferase	Total bilirubin
Sodium	Creatinine
Alkaline phosphatase	Glucose
Potassium	Albumin
Gamma-glutamyl transferase	Total protein
Thyroid-stimulating hormone	Lactate dehydrogenase
Thyroxine, Free	

Hematology

Hemoglobin	Neutrophils
Hematocrit	Lymphocytes
Red blood cells	Monocytes
Platelet count	Eosinophils
White blood cell count – total and differential	Basophils
Mean corpuscular hemoglobin	Neutrophils Band Forms
Mean corpuscular hemoglobin concentration	Mean corpuscular volume

Urinalysis

Glucose	pH
Specific gravity	Urobilinogen
Blood	Color
Ketones	Leukocyte esterase
Protein	Nitrite
Bilirubin	

Microscopic examination will be conducted if protein and/or blood is/are detected during urinalysis. At a minimum the microscopic examination will consist of red blood cells, white blood cells, casts, and bacteria.

Clinical laboratory test values are potentially clinically important (PCI) if they meet either the low or high PCI criteria. The PCI criteria are listed in [Table 4](#) for subjects aged 4-5 years and [Table 5](#) for subjects aged 6-12 years. The number and percentage of subjects with post-baseline PCI values will be tabulated. The percentages will be calculated relative to the number of subjects with available baseline values and at least 1 post-baseline assessment. The numerator is the total number of subjects with at least 1 post-baseline PCI value. A supportive listing of subjects with post-baseline PCI values will be provided including the subject number, baseline, and post-baseline values.

Table 4 Criteria for Potentially Clinically Important Laboratory Tests for Subjects Aged 4-5 Years

Parameter	SI Unit	Lower Limit	Higher Limit
Biochemistry			
Albumin	g/L	< 30g/L	-
Aspartate transaminase (AST)	-	-	>3 x ULN
Alanine transaminase (ALT)	-	-	> 3 x ULN
Alkaline phosphatase			>2.5 x ULN
Blood urea nitrogen	mmol/L	-	> 10.7mmol/L or > 2.5 x ULN
Calcium	mmol/L	< 2	> 2.9
Total cholesterol	mmol/L	-	> 7.8
Creatinine	µmol/L	-	> 176.8 µmol/L or > 1.5 x ULN
Gamma glutamyl transferase	-	-	≥ 2.5 x ULN
Glucose	mmol/L	< 3.1	> 8.9
Lactate dehydrogenase	-	-	> 3 x ULN
Phosphorus, inorganic	mmol/L	< 0.8	> 2.3
Potassium	mmol/L	< 3.0	> 5.5
Thyroid stimulating hormone	-	< LLN	> 2 x ULN
Sodium	mmol/L	< 130	> 150
Urate	µmol/L	-	> 594.8
Bilirubin, total	µmol/L	-	> 34.2
Total protein	g/L	< 50	> 90
Hematology			
Neutrophils Band Form	-	-	> 0.27x10 ³ /µL or > 5%
Basophils	-	-	> 10%
Hemoglobin	g/L	< 90	> 160
Hematocrit	%	< 30%	> 50%
Platelet count	10 ⁹ /L	< 75	> 600

Table 4 Criteria for Potentially Clinically Important Laboratory Tests for Subjects Aged 4-5 Years

Parameter	SI Unit	Lower Limit	Higher Limit
Red blood cells	10 ¹² /L	< 2.5	> 7.5
White blood cell count	10 ⁹ /L	< 3	> 16.0
Neutrophils	10 ⁹ /L	< 1x10 ⁹ /L or < 30%	> 6.2 10 ⁹ /L or > 70%
Eosinophils	10 ⁹ /L OR %	-	0.5 x 10 ⁹ /L or > 10%
Lymphocytes	%	< 10%	> 70%
Monocytes	%	-	> 20%
Urinalysis			
Glucose	-	-	Positive Value (excluding trace)
Protein	-	-	Positive Value (excluding trace)
Blood	-	-	Positive Value (excluding trace)
Ketones	-	-	Positive Value (excluding trace)
Bilirubin	-	-	Positive Value (excluding trace)
Leukocyte Esterase			Positive Value (excluding trace)
Nitrite			Positive Value (excluding trace)

LLN: Lower limit of normal value provided by the laboratory

ULN: Upper limit of normal value provided by the laboratory

Age is calculated from the informed consent date from antecedent studies for Group A and from the informed consent date from SHP465-308 for Group B.

Table 5 Criteria for Potentially Clinically Important Laboratory Tests for Subjects Aged 6-12 Years

Parameter	PCI Criteria
Biochemistry	
Cholesterol-H	>300mg/dl** (>7.8mmol/L)
Glucose, serum	<55mg/dl or >160mg/dl (<3.1mmol/L or >8.9mmol/L)
Bilirubin, total	>1.5 x ULN
Transaminase, SGOT, AST	>3 x ULN
Transaminase, SGPT, ALT	>3 x ULN
Gamma Glutamyl Transpeptidase (GGT)	>3 x ULN
Alkaline phosphatase	>2.5 x ULN
Lactate dehydrogenase (LDH)	>3 x ULN*
Sodium	<130mEq/L (grade 3) or >150mEq/L (mmol/L)
Potassium, serum/plasma	<3mEq/L (grade 3) or >5.5mEq/L (mmol/L)
Calcium	<8mg/dl or >11.5mg/dl (<2mmol/L or >2.9mmol/L)
Phosphorus, inorganic	<2.5mg/dl or >7.0mg/dl** (<0.8mmol/L or >2.3mmol/L)
Urate	>10mg/dl (>0.6mmol/L or >594.8µmol/L)
Thyroid Stimulating Hormone (TSH) ~	< 0.35 µIU/ml or > 6 µIU/mL (0.35mIU/L or >6mIU/L)
Blood Urea nitrogen (BUN)	>2.5 x ULN* (or alternatively >30mg/dl**, >10.7mmol/L)
Creatinine, serum	>1.5 x ULN (or alternatively >2mg/dl**, >176.8µmol/L)
Albumin	<3g/dl (<30g/L)
Total protein, plasma or serum	<5g/dl* or >9g/dl* (<50g/L or >90g/L)
Hematology	
Hemoglobin (He.)	<10g/dl (<100g/L)
Hematocrit	<32% or >45% (<0.32 or >0.45 Fraction of 1)
Blood Cells (RBC)	male: <2.5 x 10 ⁶ /µL; female: <2.0 x 10 ⁶ /µL (male: <2.5 x 10 ¹² /L; female: <2.0 x 10 ¹² /L)
Mean Corpuscular Hemoglobin (MCH)~	< 27pg or > 32pg
Mean Corpuscular Volume (MCV)~	< 70fL or > 110fL
Mean Corpuscular He. Concentration (MCHC)~	< 28g/dL or > 41g/dL (<280g/L or >410g/L)
Platelet count	<75 x 10 ⁹ /L or >500 x 10 ⁹ /L

Table 5 Criteria for Potentially Clinically Important Laboratory Tests for Subjects Aged 6-12 Years

Parameter	PCI Criteria
Biochemistry	
White Blood Cell Count (WBC)	<3 x 10 ⁹ /L or >16 x 10 ⁹ /L
Neutrophils Band Form	> 5%
Neutrophils	< 15%
Eosinophils	> 10%
Basophils	> 15%
Lymphocytes	> 80%
Monocytes	> 40%
ANC (%neutrophils x WBC count)	<1.3x10 ⁹ /L
Urinalysis	
Glucose	Positive Value (excluding trace)
Blood	Positive Value (excluding trace)
Ketones	Positive Value (excluding trace)
Protein	Positive Value (excluding trace)
Bilirubin	Positive Value (excluding trace)
Leukocyte Esterase	Positive Value (excluding trace)
Nitrite	Positive Value (excluding trace)

*The NCI has not specified a value, Shire physicians have agreed on lab values provided.

** Values taken from the Reviewer Guidance, Conducting a Clinical Safety Review of a New Product Application and Preparing a Report on the Review, Table 7.1.7.3.2.1 pp 70-72. US DHHS FDA CDER, February 2005.

-These values were taken from Clinical Laboratory Diagnostics, ed. L. Thomas, MD, Frankfurt, Germany, 1998.

ULN: Upper limit of normal value provided by the laboratory

Age is calculated from the informed consent date from antecedent studies for Group A and from the informed consent date from SHP465-308 for Group B.

All laboratory data will be listed for the Safety Set.

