Vital sign values will be considered PCI if they meet the criteria listed in [Table 6](#) for Age 4-5 or if they meet the criteria in [Table 7](#) for Age 6-12. The number and percentage of subjects with PCI post-baseline values will be summarized. The percentages will be calculated relative to the number of subjects with baseline and at least 1 post-baseline assessment. The numerator is the total number of subjects with at least 1 PCI post-baseline vital sign value. A supportive listing of subjects with post-baseline PCI values will be provided including the treatment group of the antecedent studies, subject number, site, baseline, and post-baseline PCI values. A listing of all AEs for subjects with post-baseline PCI vital sign values will also be provided.

Table 6 Criteria for Potentially Clinically Significant Vital Sign Findings in Subjects Aged 4-5 Years

Vital Sign Parameter	Flag	Criteria ^a	
		Observed Value	Change from Baseline
Sitting Systolic blood pressure (mmHg)	High	≥120	Increase of >10
	Low	<75	Decrease of >10
Sitting Diastolic blood pressure (mmHg)	High	≥85	Increase of >10
	Low	<40	Decrease of >10
Pulse rate (beats per minute)	High	≥130	Increase of >15
	Low	≤55	Decrease of >15
Weight (kg)	High	-	Increase of ≥7%
	Low	-	Decrease of ≥7%
Temperature (deg. C)	High	>39	-
	Low	<35	-
BMI (kg/m ²)	High	>95th percentile for age and sex	-
	Low	<5th percentile for age and sex	-

^a A post-baseline value is considered a PCI finding if its meets either the criteria for observed value or the criteria for the change from baseline.

Age is calculated from the informed consent date from antecedent studies for Group A and from the informed consent date from SHP465-308 for Group B.

Table 7 Criteria for Potentially Clinically Significant Vital Sign Findings for Subjects Aged 6-12 Years

Vital Sign Parameter	PCI Criteria
Weight Loss (kg)	≥7% of weight (determined at baseline)
Systolic BP (mmHg), seated, 6 – 12 years~	>120* >120* on 2 or more consecutive visits >10 increase from baseline >10 increase from baseline on 2 or more consecutive visits >120* and increase >10 from baseline >120* and increase >10 from baseline on 2 or more consecutive visits
Diastolic BP (mmHg), seated, 6 – 12 years~	>80* >80* on 2 or more consecutive visits >10 increase from baseline >10 increase from baseline on 2 or more consecutive visits

Table 7 Criteria for Potentially Clinically Significant Vital Sign Findings for Subjects Aged 6-12 Years

Vital Sign Parameter	PCI Criteria

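### Laboratory PCI percentages, and a few for vital signs, count subjects who already met the observed-value criterion at baseline

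*SAP*

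**What the plan says.** **Laboratory tests (SAP 11.2).** "Clinical laboratory test values are potentially clinically important (PCI) if they meet either the low or high PCI criteria". Tables 4 and 5 set those limits on the observed value, and baseline is not part of any of them. "The percentages will be calculated relative to the number of subjects with available baseline values and at least 1 post-baseline assessment", and "The numerator is the total number of subjects with at least 1 post-baseline PCI value". Two other outputs show baseline. One is a listing: "A supportive listing of subjects with post-baseline PCI values will be provided including the subject number, baseline, and post-baseline values". The other is a set of shift tables: "shift tables from Baseline to Visit 16/ET for quantitative variables will be presented".

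**Vital signs (SAP 11.3).** The structure is the same. The denominator needs a baseline and a post-baseline value, and "The numerator is the total number of subjects with at least 1 PCI post-baseline vital sign value". Footnote a of Table 6 (ages 4-5) accepts either the observed value or the change from baseline. Table 7 (ages 6-12) has separate rows for observed values, for change, and for both combined.

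**Which values feed PCI.** SAP 18.4 uses all post-baseline assessments, including repeat and unscheduled ones. The protocol schedule for Group B places on-treatment laboratory tests at Month 6 and Month 12.

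**The concern.** The denominator requires a baseline value, yet the rule does not use it to separate a value that became abnormal on treatment from one that was abnormal all along. The study has no control arm and safety is its primary objective, so readers will tend to take these percentages as a description of what happened on drug. A child with a positive urine ketone or blood result before the first dose and again at Month 6 adds one to the numerator, just as a child whose result turned positive on treatment does.

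The SAP is more careful elsewhere. In SAP 11.1 an adverse event that began before dosing becomes treatment-emergent only if its severity increases. In Table 11 the ECG-result criterion for ages 6-12 is defined as a shift from baseline.

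**Working it through.** The plan states no PCI rate, no baseline PCI prevalence and no count of missing baselines, so there is no figure to reproduce. The check has two parts.

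**1. Which criteria are affected**

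- *Laboratory, Tables 4 and 5:* affected. Protocol exclusion 13 removes clinically significant laboratory abnormalities. That is a judgement and is not tied to the PCI limits, so PCI values at baseline remain possible.
- *Urinalysis positives:* most exposed. They are qualitative, so the shift tables do not cover them.
- *Limits that appear close to normal:* MCH below 27 or above 32 pg (Table 5) and neutrophils below 30% or above 70% (Table 4). The documents do not print the laboratory's reference ranges, so closeness is a judgement. For comparison, Table 5 flags neutrophils only below 15%.
- *Month 6 and unscheduled laboratory values:* they count towards PCI, but the shift tables go only to Visit 16/ET.
- *Table 6 systolic 120 or more and diastolic 85 or more (ages 4-5):* cannot be met at entry by an eligible child. Exclusion 6 removes blood pressure at or above the 95th percentile, and the largest Table 9 values at ages 4-5 are 116 and 74 mmHg.
- *Table 6 pulse limits and low blood pressure limits:* affected in principle. The entry criteria set no pulse limit and no lower blood pressure limit.
- *Table 7 blood pressure and pulse:* combined rows already condition on change from baseline.
- *Temperature and respiratory rate:* scheduled only at screening or baseline, so few post-baseline values should exist.
- *BMI:* the Table 6 cut-off ">95th percentile for age and sex" is observed-value, but SAP 11.3 also plans shifts in BMI percentile category from baseline at each visit.
- *Change-from-baseline criteria:* cannot be met at baseline.

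**2. How far the percentage can move**

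Notation:
- D = subjects with a baseline and at least one post-baseline value
- b = share meeting the criterion at baseline
- s = probability of a post-baseline PCI value if PCI at baseline
- i = the same probability if not PCI at baseline
- m = subjects with a post-baseline value but no baseline
- q = the PCI rate among those m subjects

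Formulas:
- Rate as literally written = [D·b·s + D·(1−b)·i + m·q] / D
- Rate with the numerator inside the denominator = b·s + (1−b)·i
- Newly occurring rate = i, on D·(1−b) subjects
- Excess of the literal rate over the newly occurring rate = b·(s − i) + m·q/D

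D = 80 is the SAP 2.5 enrolment target and is used only for scale. All other inputs are assumed. With i = 3%, m = 0 and s from 0.5 to 1:

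| b | Rate as written | Newly occurring |
|---|---|---|
| 0% | 3.0% | 3.0% |
| 2% | 3.9% to 4.9% | 3.0% |
| 5% | 5.4% to 7.9% | 3.0% |
| 10% | 7.7% to 12.7% | 3.0% |

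For example, b = 5% and s = 1 gives 0.05 × 1 + 0.95 × 0.03 = 0.0785.

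In whole numbers, 4 subjects PCI at baseline and afterwards plus 2 newly PCI give 6/80 = 7.5% as written. The newly occurring rate is 2/(80 − 4) = 2/76 = 2.6%. With i = 0, b = 5% and s = 1, the table shows 5.0% although nothing new occurred.

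Adding m = 2 subjects without a baseline, with q set to the overall rate, raises the literal figure by only 0.1 to 0.3 points at D = 80. In a column of D = 20 the rise is 0.3 to 1.3 points.

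**The case against.** The case for leaving the plan alone has real content.

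- **Labelling.** The SAP calls these values post-baseline, never new or treatment-emergent. A reader might infer that it presents pre-existing abnormalities as drug effects. It does not say so, and no formal tests are planned.
- **Scope.** A reader might infer that every PCI percentage is affected. The first part of the working shows otherwise. In addition, SAP 11.4 requires no baseline for observed-value ECG percentages, so the mismatch between numerator and denominator does not arise there.
- **BMI.** It is tempting to argue that 5% of a reference population lies above the 95th percentile, so at least 2 of 40 children aged 4-5 must be flagged with no change. The documents do not support this. It would be an expected count (0.05 × 40 = 2) only if the sample matched the reference population; it is not a minimum, and the planned percentile shifts already show who was above the cut-off at baseline.
- **Denominator.** Read literally, a subject without a baseline could enter the numerator but not the denominator. A percentage of a set is normally computed within that set, and the effect is small. This is a wording gap.
- **Entry screening.** Several laboratory limits are extreme, such as AST or ALT above 3 × ULN, and will seldom be met at baseline.

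What remains is the laboratory gap. The listing shows baseline values but does not change a summary percentage. The shift tables leave out qualitative urinalysis, Month 6 and unscheduled values. The SAP also does not say whether their categories match the PCI limits.

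**Conclusion.** The point holds in limited form, as an inexpensive reporting improvement. For observed-value laboratory criteria, and for the few vital-sign rows without a baseline-conditioned companion, the planned percentage mixes persisting and newly occurring values although the baseline needed to separate them is already required. The size depends on baseline PCI prevalence and persistence, which the documents do not give. The contrast of 7.5% with 2.6% is an illustration on assumed counts, not an estimate for this trial. The enrolment target of 80 is itself uncertain as a denominator: the protocol says about 145, and the study was terminated early.

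**What to change.** In SAP 11.2 and 11.3, state that the numerator counts only subjects who are in the denominator. For each affected observed-value criterion, add one row beside the current one: n/N with a post-baseline PCI value among subjects who did not meet that criterion at baseline.

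Keep the current row. SAP 11 takes the last value before the first dose in this study as the safety baseline. For Group A that can fall after exposure to SHP465 in the antecedent study (all of SHP465-112 and the active arm of SHP465-309). A row restricted to new values alone could hide an abnormality that began there.

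The cost is one extra row per criterion and smaller denominators in the new rows, most noticeably in the individual reporting columns. No new data are needed.

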11.3 Vital Signs (Including Height and Weight)

The averaged values of the 3 measurements collected for blood pressure and pulse at each visit will be used for all summaries and determination of PCIs. Summaries for vital signs will be presented by treatment group of the antecedent studies, current treatment (SHP465) for each enrollment type, and overall.

Descriptive statistics for vital signs (sitting systolic and diastolic blood pressure, pulse and weight) and their changes from baseline at each post-baseline visit and FoTA will be presented in a summary table. These summaries will also include BMI. BMI will be automatically

calculated using the height and weight collected at each visit. In the case of multiple assessments at post-baseline visits, the first readable value at the visit will be used in the summary tables.

Additionally, figures with the mean change from baseline \pm SD of the vital signs values (sitting systolic and diastolic blood pressure, and pulse) will be presented by visit for each treatment group of the antecedent studies and current treatment (SHP465) for each enrollment type.

Height, weight and BMI will also be converted to percentile values based on the subject's age and sex at each visit and summarized categorically (<5th, 5th to <95th, and \geq 95th) at each visit and at the FoTA. Post-baseline shifts in height, weight and BMI percentile category (<5th, 5th to <95th, and \geq 95th) from baseline will be summarized at each visit and at the FoTA. In addition, z-scores for weight and BMI will be based on the subject's age at each visit and will be summarized categorically (<-2, \geq -2 to <-1, \geq -1 to <1, \geq 1 to <2, and \geq 2) at each visit and at the FoTA. Percentiles and z-scores will be derived using the CDC growth charts ([Kuczmarski et al. 2002](#)). A SAS program for the 2000 CDC Growth Charts will be used to derive the percentiles and z-scores (www.cdc.gov/nccdphp/dnpao/growthcharts/resources/sas.htm).

Vital sign values will be considered PCI if they meet the criteria listed in [Table 6](#) for Age 4-5 or if they meet the criteria in [Table 7](#) for Age 6-12. The number and percentage of subjects with PCI post-baseline values will be summarized. The percentages will be calculated relative to the number of subjects with baseline and at least 1 post-baseline assessment. The numerator is the total number of subjects with at least 1 PCI post-baseline vital sign value. A supportive listing of subjects with post-baseline PCI values will be provided including the treatment group of the antecedent studies, subject number, site, baseline, and post-baseline PCI values. A listing of all AEs for subjects with post-baseline PCI vital sign values will also be provided.

Table 6 Criteria for Potentially Clinically Significant Vital Sign Findings in Subjects Aged 4-5 Years

Vital Sign Parameter	Flag	Criteria ^a	
		Observed Value	Change from Baseline
Sitting Systolic blood pressure (mmHg)	High	≥120	Increase of >10
	Low	<75	Decrease of >10
Sitting Diastolic blood pressure (mmHg)	High	≥85	Increase of >10
	Low	<40	Decrease of >10
Pulse rate (beats per minute)	High	≥130	Increase of >15
	Low	≤55	Decrease of >15
Weight (kg)	High	-	Increase of ≥7%
	Low	-	Decrease of ≥7%
Temperature (deg. C)	High	>39	-
	Low	<35	-
BMI (kg/m ²)	High	>95th percentile for age and sex	-
	Low	<5th percentile for age and sex	-

^a A post-baseline value is considered a PCI finding if its meets either the criteria for observed value or the criteria for the change from baseline.

Age is calculated from the informed consent date from antecedent studies for Group A and from the informed consent date from SHP465-308 for Group B.

Table 7 Criteria for Potentially Clinically Significant Vital Sign Findings for Subjects Aged 6-12 Years

Vital Sign Parameter	PCI Criteria
Weight Loss (kg)	≥7% of weight (determined at baseline)
Systolic BP (mmHg), seated, 6 – 12 years~	>120* >120* on 2 or more consecutive visits >10 increase from baseline >10 increase from baseline on 2 or more consecutive visits >120* and increase >10 from baseline >120* and increase >10 from baseline on 2 or more consecutive visits
Diastolic BP (mmHg), seated, 6 – 12 years~	>80* >80* on 2 or more consecutive visits >10 increase from baseline >10 increase from baseline on 2 or more consecutive visits

Table 7 Criteria for Potentially Clinically Significant Vital Sign Findings for Subjects Aged 6-12 Years

Vital Sign Parameter	PCI Criteria
	>80* and increase >10 from baseline >80* and increase >10 from baseline on 2 or more consecutive visits
Pulse (beats/minute)	<=50* <=50* and decrease >15 from baseline >=100* >=100* on 2 or more consecutive visits >=100* and increase >15 from baseline >=100* and increase >15 from baseline on 2 or more consecutive visits
Temperature (tympanic)	>38.0°C (100.4°F)
Temperature (oral)	>37.5°C (99.5°F)
Respiratory Rate (breaths per minute)	<10 or >24

~Given the pharmacological effect of the drugs used in ADHD and based on experience gained in previous ADHD trials, the focus is on rise of blood pressure only.

*The NCI has not specified a value, Shire physicians have agreed on values provided.

Age is calculated from the informed consent date from antecedent studies for Group A and from the informed consent date from SHP465-308 for Group B.

Pulse rate (beats per minute) will be considered abnormal if a value is lower than the 1st percentile or higher than the 99th percentile cut-off values listed in [Table 8](#).

Table 8 Normal Range of Pulse Rate (beats/min)

Age	1 st Percentile	99 th Percentile
	Males	
4-5 years	69	120
6-8 years	59	114
9-11 years	56	110
12 years	52	108
	Females	
4-5 years	70	132
6-8 years	61	117
9-11 years	58	113
12 years	54	110

Source: National health statistics report: Resting Pulse Rate Reference Data for Children, Adolescents, and Adults: United States, 1999–2008

<https://www.cdc.gov/nchs/data/nhsr/nhsr041.pdf>

The number and percentage of subjects with abnormal pulse rate values for at least 1 post-baseline assessment will be tabulated by treatment group of the antecedent studies, current treatment (SHP465) for each enrollment type, and overall for the lower than the 1st percentile

and higher than the 99th percentile cut-off values, respectively, for male and female separately. The denominator will be the number of subjects in the Safety Set (per gender) with at least 1 post-baseline pulse measurement. The numerator is the total number of subjects with at least 1 abnormal pulse record. A supportive listing of subjects with abnormal pulse rate values will be provided.

In addition, following the US Department of Health and Human Services standards, blood pressure values higher than the 95th percentile determined by sex, age, and height percentiles will be considered abnormal. The cut-off values are presented in [Table 9](#). If a height percentile falls between the listed percentiles, as a conservative approach the lower end of the percentiles will be used to identify the corresponding 95th percentile of blood pressures. If a height percentile is less than 5th percentile, the 5th percentile will be used to identify the corresponding 95th percentile of blood pressures.

Table 9 95th Percentile Cut-off Values of Blood Pressure Norms by Sex, Age, and Height Percentiles

Age (y)	Systolic Blood Pressure (mmHg)							Diastolic Blood Pressure (mmHg)							
	Percentile of Height							Percentile of Height							
Boys															
	5%	10%	25%	50%	75%	90%	95%		5%	10%	25%	50%	75%	90%	95%
4	106	107	109	111	112	114	115		66	67	68	69	70	71	71
5	108	109	110	112	114	115	116		69	70	71	72	73	74	74
6	109	110	112	114	115	117	117		72	72	73	74	75	76	76
7	110	111	113	115	117	118	119		74	74	75	76	77	78	78
8	111	112	114	116	118	119	120		75	76	77	78	79	79	80
9	113	114	116	118	119	121	121		76	77	78	79	80	81	81
10	115	116	117	119	121	122	123		77	78	79	80	81	81	82
11	117	118	119	121	123	124	125		78	78	79	80	81	82	82
12	119	120	122	123	125	127	127		78	79	80	81	82	82	83
Girls															
4	105	106	107	108	110	111	112		68	68	69	70	71	71	72
5	107	107	108	110	111	112	113		70	71	71	72	73	73	74
6	108	109	110	111	113	114	115		72	72	73	74	74	75	76
7	110	111	112	113	115	116	116		73	74	74	75	76	76	77
8	112	112	114	115	116	118	118		75	75	75	76	77	78	78
9	114	114	115	117	118	119	120		76	76	76	77	78	79	79
10	116	116	117	119	120	121	122		77	77	77	78	79	80	80
11	118	118	119	121	122	123	124		78	78	78	79	80	81	81
12	119	120	121	123	124	125	126		79	79	79	80	81	82	82

Source: National Heart Lung and Blood Institute; May 2004
http://www.nhlbi.nih.gov/guidelines/hypertension/child_tbl.htm

The number and percentage of subjects with any post-baseline blood pressure values higher than the 95th percentile (exclusive) will be tabulated by gender and treatment group of the antecedent studies, current treatment (SHP465) for each enrollment type, and overall. The denominator will be the number of subjects in the Safety Set (per gender) with at least 1 post-Baseline blood pressure measurement. The numerator will be the total number of subjects with at least 1 blood pressure value higher than the 95th percentile. A supportive listing of all subjects with abnormal blood pressure values will be provided.

All vital signs data will be listed for the safety Set.

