## 9.9 Safety Analyses

Safety assessments include the occurrence of TEAEs and evaluations of blood pressure, pulse, height, weight, BMI, results of clinical laboratory evaluations and ECG, sleep questionnaires (PSQ and CSHQ), and C-SSRS.

The safety set will be used to report the safety data. Safety analyses will be presented by treatment group of the antecedent studies and overall.

Adverse events will be coded using the Medical Dictionary for Regulatory Activities. Treatment emergent AEs are defined as AEs that started or deteriorated on or after the date of the first dose of investigational product, and no later than 3 days following the last dose of investigational product. The number of events, incidence, and percentage of TEAEs will be calculated overall, by system organ class, by preferred term, and by treatment group. Treatment emergent AEs will be further summarized by severity and relationship to investigational product. Adverse events related to investigational product, AEs leading to withdrawal, SAEs, and deaths will be similarly summarized/listed.

Clinical laboratory tests, vital signs, and ECG findings will be summarized by visit. Potentially clinically important findings will also be summarized or listed.

The PSQ and CSHQ will be summarized using appropriate descriptive statistics at each visit.

The C-SSRS results will be summarized and listings of the C-SSRS data will be provided for subjects with a positive response.

In addition, the safety data on TEAEs will also be descriptively summarized by treatment within each age (4-5 years and 6-12 years), sex, race (white and non-white), and ethnicity subgroup.

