3. OBJECTIVES

3.1 Primary Objective

The primary objective is to evaluate the long-term safety and tolerability of SHP465 at 6.25mg administered as a daily morning dose in children aged 4-12 years (inclusive at the time of consent) diagnosed with Attention-deficit/Hyperactivity Disorder (ADHD).

The evaluation of safety and tolerability will be based on the occurrence of treatment-emergent adverse events (TEAEs), evaluation of vital signs (systolic and diastolic blood pressure and pulse), weight, height, body mass index (BMI); clinical laboratory and electrocardiogram (ECG) results; sleep assessment (Post Sleep Questionnaire [PSQ], and Children's Sleep Habits Questionnaire [CSHQ]); and responses to the Columbia-Suicide Severity Rating Scale (C-SSRS).

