11. SAFETY ANALYSES

Safety data will be analyzed for the Safety Set by treatment group of the antecedent studies, current treatment (SHP465) for each enrollment type, and overall. Safety endpoints include the occurrence of TEAEs, vital signs (systolic and diastolic blood pressure, and pulse), height, weight, body mass index (BMI); clinical laboratory and ECG results, C-SSRS, and sleep questionnaires (PSQ and CSHQ). For each safety endpoint, the last value collected before the first dose of investigational product in this study will be used as baseline for all analyses of that safety endpoint. Except for adverse event data, only post-baseline assessments from Visit 2 (Week 0) up to Visit 16 (Month 12) that were collected on or 2 days after the last dose of investigational product will be analyzed. A Final on-Treatment Assessment (FoTA) will be defined as the last valid assessment obtained after Baseline and whilst on investigational product (on or before 2 days after the last dose date).

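### After baseline, SAP 11.3 summarises height only in three broad percentile bands and shifts between them; a mean change in height z-score would be more sensitive at almost no cost.

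*SAP*

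**What the plan says.** Height belongs to the primary objective. SAP 3.1 bases the safety evaluation on "evaluation of vital signs (systolic and diastolic blood pressure and pulse), weight, height, body mass index (BMI") among other items, SAP 11 lists the endpoints as "vital signs (systolic and diastolic blood pressure, and pulse), height, weight, body mass index (BMI") and more, and Protocol 9.9 likewise names "evaluations of blood pressure, pulse, height, weight, BMI". Protocol 7.2.3.5 has height measured at baseline and at each monthly treatment visit.

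SAP 11.3 then treats the measures differently:

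- Continuous summaries: "Descriptive statistics for vital signs (sitting systolic and diastolic blood pressure, pulse and weight) and their changes from baseline", at each post-baseline visit and at the final on-treatment assessment (FoTA). BMI is added. Height appears in that paragraph only as an ingredient of BMI, which is "calculated using the height and weight collected at each visit".
- Percentiles: height, weight and BMI are placed in three bands (<5th, 5th to <95th, >=95th), and "Post-baseline shifts in height, weight and BMI percentile category" are tabulated at each visit and at FoTA.
- Z-scores: "In addition, z-scores for weight and BMI will be based on" age at each visit, in five bands. Height is not named.
- Source: "Percentiles and z-scores will be derived using the CDC growth charts", using a named SAS program.

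SAP Tables 6 and 7 contain no height criterion. The only continuous height summary is the baseline characteristic in SAP 7.1.

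**The concern.** Of the three body-size measures in the primary objective, height alone has no planned continuous summary after baseline, and no reason is given. Three bands are a blunt tool for growth. The middle band holds most children, and exclusion criterion 7 (Protocol 4.2) keeps out those at or below the 5th percentile, so the lowest band should be almost empty at the start. A child can lose a good deal of height-for-age without changing band. At stake is whether the report could show a modest average slowing of growth over up to 12 months, or could give a useful bound on it.

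**Working it through.** The documents give no figure for height change, so there is nothing to reproduce. The check has a textual part and an illustration on assumed inputs.

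**1. What is planned after baseline (SAP 11.3)**

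| Measure | Mean change | Percentile bands and shifts | Z-score bands |
|---|---|---|---|
| Blood pressure, pulse | yes | no | no |
| Weight | yes | yes | yes |
| BMI | yes | yes | yes |
| Height | no | yes | no |

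No other SAP section fills the gap for height. SAP 7.1 covers baseline only, the closing line of 11.3 promises listings, and 18.1 gives a format for continuous variables without saying which are summarised.

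**2. Width of the middle band.** The 5th and 95th percentiles lie at z = -1.645 and +1.645, so the width is 2 x 1.645 = 3.29 SD.

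**3. How many children change band.** Assumptions, not from the documents: baseline height z is standard normal, truncated at the 5th percentile by the entry criterion; every child falls by the same d.

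- Newly below the 5th: (Phi(-1.645 + d) - 0.05) / 0.95
- Leaving the top band: (Phi(1.645 + d) - 0.95) / 0.95

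| d (SD) | Newly <5th | Leave >=95th | Same band |
|---|---|---|---|
| 0.1 | 1.2% | 1.0% | 97.8% |
| 0.25 | 3.3% | 2.2% | 94.5% |
| 0.5 | 8.0% | 3.6% | 88.4% |

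With 60 children (the number meant to complete 6 months in Protocol 9.6 and SAP 2.5) and d = 0.25, this is 60 x 0.0332 = 2.0 newly below the 5th and 60 x 0.0220 = 1.3 leaving the top band.

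**4. Precision of a mean z-change.** The half-width of the 95% CI is t(0.975, n-1) x s / sqrt(n), where s is the SD of individual z-change, assumed to be 0.2 to 0.5.

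- n = 60: 2.001 x 0.2 / 7.746 = 0.052, up to 2.001 x 0.5 / 7.746 = 0.129.
- n = 40 (Protocol 9.6 target for ages 4-5): 0.064 to 0.160.
- n = 145 (Protocol 9.6 enrolment): 0.033 to 0.082.

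**5. Rough comparison of the two readings.** Let z1 = z0 - d + N(0, s), with s = 0.2, 0.3 or 0.5. Call a band count notable if it exceeds the 95th percentile of its distribution at d = 0. This yardstick belongs to this review; the SAP plans no test.

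| n, d | <5th count notable | Downward-shift count notable | 95% CI of mean z-change excludes 0 |
|---|---|---|---|
| 60, 0.25 | 20-41% | 27-48% | 97% or more |
| 60, 0.5 | 67-90% | 76-94% | close to 100% |
| 145, 0.25 | 49-66% | 51-86% | close to 100% |
| 145, 0.5 | 97% or more | 98% or more | close to 100% |

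Because counts are discrete, the yardstick's false-signal rate is not matched to the 2.5% of the CI's lower side. At n = 60 the binomial tail at d = 0 is 1.9-2.6% for the <5th count (per-child probabilities 0.0106, 0.0176, 0.0351; limits 2, 3, 5). At n = 40 it is 0.9-3.3%. The table gives the direction and rough size of the gap, not exact probabilities.

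**The case against.** The strongest reply is that this may be a drafting slip rather than a choice. The heading of SAP 11.3 includes height, and the percentile sentence says height is converted in addition to something, as though it had already been summarised. SAP 1 and 20 place table specifications and templates in separate documents that were not supplied, and these may contain a height-change table. That stands, so the point is confined to the SAP text. If the shells already cover height, the remedy is to align the wording.

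A second reply is that nothing here conflicts with the protocol, which asks that height be summarised and specifies neither mean change nor z-score. Percentile bands at every visit meet that request, and all vital signs are listed. This also stands: the point is about sensitivity, not non-compliance.

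A third is that mean centimetres gained by growing children, without a control arm, say little about slowed growth. This is right, and it is why the age- and sex-standardised z-score is the measure to add.

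A reader might infer that height goes unanalysed or that growth suppression would be hidden. The documents do not support either. Height is summarised at baseline and in bands at each visit, and a large fall would usually be visible.

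**Conclusion.** The point holds as a free improvement. On the SAP text, the only post-baseline summaries of height are three percentile bands and their shifts, and under the assumptions in steps 3 to 5 these would mostly miss a modest average fall. At 0.25 SD about 94% of children stay in the same band, whereas with 60 children the CI half-width for mean z-change would be about 0.05 to 0.13. The advantage shrinks at 145 children and is small for a fall near 0.5 SD.

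The effect sizes, the SD of z-change and the baseline distribution are all assumed. The numbers of children are targets; SAP 1 records a decision to terminate the study on 14 Dec 2018, so late visits may hold fewer.

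It would be tempting to read a CI excluding zero as a drug effect on growth. The design does not allow that. There is no control arm, SAP 2.6 plans no formal tests, and such an interval would show only a departure from the CDC reference. SAP 2.1 also shows that Group A children from SHP465-112, and those given active drug in SHP465-309, had taken SHP465 before entering this study.

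**What to change.** In SAP 11.3:

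- Derive the CDC height-for-age z-score by age and sex at each visit with the SAS program already named.
- Report n, mean, SD and 95% CI of its change from baseline at each visit and at FoTA, for the Total column and by age group (4-5 and 6-12 years).
- Name the baseline. Use the SAP 11 safety baseline (last value before the first dose in this study) and state it explicitly for Group A, because SAP 2.1 and part of 7.1 point to the antecedent study's baseline instead. Add a note that some Group A children had prior SHP465 exposure.
- Raw height change may be added for completeness, but it is not the informative measure.
- Keep the existing band and shift tables, and interpret everything descriptively.

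The cost is some SAP wording and a few table rows. No new data, visits or software are needed: height is already used to derive BMI and percentiles. SAP 10.2.1 already gives a 95% CI with mean change for ADHD-RS-5, although that is an efficacy measure and SAP 11 plans no interval for any safety variable.
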